#### 3.1.4.1 Other Measures of Dialysis Adequacy

All patients in both arms of the study will have dialysis dose measured by a number of different methods, including urea kinetics, creatinine kinetics, and phosphate kinetics. Phosphate clearance will be calculated by the method of Gotch. [Gotch, 2003] Pre- and post-dialysis blood samples will be obtained according to current National Kidney Foundation K/DOQI Hemodialysis Adequacy guidelines [NKF-K/DOQI Clinical Practice Guidelines for Hemodialysis Adequacy: update 2000, 2001].

#### 3.1.5 Residual Renal Function

Residual renal function will be measured prior to a modeling session during baseline and during follow-up at Month 4 and Month 12 for all subjects who produce urine. Timed urine collections of at

least 18 hours will be obtained during the interdialytic interval preceding a dialysis session, preferably midweek. Aliquots will be shipped to the local laboratory of the dialysis unit for measurement of urea, creatinine, and phosphorus. Predialysis blood samples from the dialysis following the collection will be shipped to the dialysis units' local laboratory for determination of pre-dialysis concentrations of urea, creatinine, and phosphorus. The time-averaged concentrations of these solutes in the blood will be obtained using kinetic modeling methods for calculation of the solute clearances. If the total volume of the collected sample is 80 ml or more, then an aliquot of the sample will be shipped to the local laboratory of the dialysis unit for measurement of urea, creatinine, and phosphorus. If the urine sample is less than 80 ml, then the patient will be considered to be anuric.

For determination of eligibility, the baseline residual renal clearance measurement will be expressed per 35 L of anthropometric volume (Watson formula)[Watson, 1980] to adjust for body size. The anthropometric volume will be used rather than modeled volume because accurate estimation of modeled volume requires averaging over several kinetic modeling sessions, which will not be possible at the first baseline assessment.

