#### 2.7 Baseline Evaluation

The purposes of the baseline evaluation are to provide subjects with further information regarding the study, collect detailed data on eligibility and exclusion criteria (including practical issues such as transportation), and document baseline characteristics and clinical information to allow stratification and assessment of important baseline prognostic variables, as well as enable pre- and post-study comparisons of specific outcomes between treatment groups. *[2014 FHN Archive Note: FHN Executive Committee dropped prognostic covariates from the analyses.]* In addition, some of the characteristics assessed will enable observational comparisons with the Nocturnal Study being conducted in parallel with this trial. The length of the baseline evaluation period will be three to fifteen weeks.

Baseline Visits will be labeled as B1 visits. The baseline assessment will include two kinetic modeling sessions, separated by at least one week (see Section 3) and labeled as the B1 and B2 visits. Key biochemical tests, including predialysis serum albumin and pre- and post-dialysis serum urea nitrogen, creatinine, and phosphorus will be obtained from local laboratories for both baseline kinetic

modeling sessions. Derived kinetic modeling parameters and the pre-dialysis albumin and phosphorus concentrations will be averaged to determine the actual assigned baseline value. A timed urine collection (minimum 18 hours) will be obtained during the interdialytic interval preceding a dialysis session, preferably midweek for subjects producing urine prior to a baseline kinetic modeling session for evaluation of the residual renal function exclusion criterion. During the baseline period, participants will also be asked to travel to and from the HD unit for 6 consecutive days (i.e., on 3 HD days and on 3 intervening non-HD days), to determine if they are able to arrange and tolerate daily travel should they be randomized to the frequent arm of the trial. On the days subjects travel to and from the dialysis unit but do not receive dialysis (before randomization), they will not be required to stay at the dialysis unit for an extended period.

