# 3.1.2 Rationale for Choosing Target Doses

# a) Conventional HD Group

HD dosing is traditionally based on clearance of urea, quantified as the Kt/V (K is the clearance of urea, t is time of dialysis session, and V is the volume of distribution of urea in the patient). Traditionally the single-pool Kt/V (spKt/V) has been used to define and measure dose in conventional HD [Gotch, 1985]. However, because the spKt/V overestimates true clearance due to the phenomenon of urea rebound, this trial will use equilibrated Kt/V (eKt/V) [Daugirdas, 1995;Pedrini, 1988]. In order to assure adherence to current national standards, a minimum eKt/V of 1.10 will be required in the conventional HD group. However, consistent with its designation as a conventional therapy arm, the dialysis prescriptions in the conventional HD group will be otherwise unspecified (subject to a minimum treatment time of 2.5 hrs).

Parameter	Conventional HD (CHD)	Daily HD (DHD)	% Difference in Medians (DHD vs. CHD)
Sessions per week	3	6	100%
Target prescription	Unspecified: $eKt/V \ge 1.10$	$eKt/(V_n) = 0.90$	-
Hours per session	$\geq 2.5$ (median = 3.50)	1.50 to 2.75 (median = 2.36)	-33%
Maximum interdialysis interval (median, hours)	68.5	45.6	-33%
Average interdialysis interval (median, hours)	52.5	25.6	-51%
Hours per week	10.5	14.2	2514
(median, $5^{th} - 95^{th}$ percentile)	(9.0-13.1)	(11.5 – 16.5)	+35%
eKt/V urea per treatment	1.39	0.92	2.40/
(median, $5^{th} - 95^{th}$ percentile)	(1.12 – 1.75)	(0.74 – 1.05)	-34%
Weekly stdKt/V urea	2.46	3.82	. 550/
(median, $5^{th} - 95^{th}$ percentile)	(2.16 – 2.80)	(3.32 – 4.17)	+55%
Weekly eKR $\beta_2$ -microglobulin (ml/min per 35 L total urea volume) (median, 5 th – 95 th percentile)	4.80 (3.77 – 6.21)	5.43 (4.26 – 6.85)	+13%
Standardized phosphorus removal (mg/day) (median, 5 th – 95 th percentile)	299 (254 - 374)	415 (338 – 497)	+39%

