# 6.2.3 Local Laboratory Measurements from Kinetic Modeling Sessions

Blood will be drawn pre and post-dialysis at each kinetic modeling session. Samples will be refrigerated and then shipped to the local laboratory associated with the dialysis unit. See Section 6.1 and Table 11 B for frequency with which various labs will be drawn. In addition, at baseline, and at the F4 and F12 visits, the patient's urine will be collected for the period in between HD sessions along with the time of collection for assessment of urea, creatinine, and phosphate excretion rates.

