## 9.8 Additional Analyses of the Effects of the Interventions

In addition to considering effects of the interventions on outcome at 4 and 12 months, contrasts will be constructed to estimate their effects on the change from 4 to 12 months to determine if treatment effects are changing over time. For quantitative outcomes obtained monthly, the basic model will be extended to evaluate patterns of change incorporating each protocol time point. Due to the larger number of time points, the covariance matrix of the residuals will be estimated under a mixed effects model including random effects (e.g., a random intercept and slope) and additional correlation parameters as needed to fit the serial correlation structure of the data [Littell, 1996;Verbeke, 1998].

Concentrations of serum albumin, hematocrit, and hemoglobin as well as blood pressure and body weight may shift shortly after initiation of daily dialysis due to altered extracellular volume, complicating interpretation of longitudinal changes. Thus, we plan to supplement tests of effects of the treatment interventions on changes from baseline to month 4 or month 12 (which may overestimate beneficial effects of the daily intervention due to hemoconcentration) with contrasts evaluating the changes from the month 1 visit, at which time most hemoconcentration effects should have occurred. Contrasts for changes from baseline to the month 1 visit will be used to estimate the size of the change in extracellular water and the associated hemoconcentration effects.

Analyses will also be used to test for interactions between the treatment interventions and prespecified baseline factors to evaluate whether certain subgroups experience increased or reduced benefits of the interventions. The Steering Committee has pre-specified the following factors for evaluation of treatment interactions:

History of heart disease, gender, anthropometric volume (Watson volume < 35 L vs.  $\ge 35$  L), years of dialysis (< 4 years vs.  $\ge 4$  years), presence of residual renal function (defined by > 100 mL urine volume per 24 hours).

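### The 80 ml anuria rule has no time base, so at Months 4 and 12 it can classify equal urine output differently by arm if urine is collected over the whole interdialytic interval

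*Protocol*

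**What the plan says.** Section 3.1.5 schedules the measurement in both arms: "Residual renal function will be measured prior to a modeling session during baseline and during follow-up at Month 4 and Month 12". The volume rule has two halves. One governs the assay: "If the total volume of the collected sample is 80 ml or more, then an aliquot of the sample will be shipped". The other gives the label: "If the urine sample is less than 80 ml, then the patient will be considered to be anuric". Neither refers to the length of the collection.

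That length is described in two ways. Section 2.7 has "A timed urine collection (minimum 18 hours) will be obtained during the interdialytic interval preceding a dialysis session", and 3.1.5 likewise asks for at least 18 hours, preferably midweek, with no upper limit. Section 6.2.3, covering baseline, F4 and F12, says "the patient's urine will be collected for the period in between HD sessions along with the time of collection".

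Section 9.8 uses a rate. Its list of baseline factors for treatment interactions includes "presence of residual renal function (defined by > 100 mL urine volume per 24 hours").

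Table 3 in section 3.1.2 gives average interdialytic intervals of 52.5 h (conventional) and 25.6 h (daily), and maximum intervals of 68.5 h and 45.6 h.

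**The concern.** A fixed volume over a variable time does not define a single level of urine output. The longer the collection, the lower the output at which a patient escapes the anuria label. At baseline this is a matter of precision, because everyone is on three sessions a week. After randomization the time available for collection is set by the assigned schedule, so the rule can work differently in the two arms.

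A patient with unchanged urine output could have clearance measured at baseline and be recorded as anuric at Month 4 after moving to daily HD, while a similar patient on conventional HD keeps a measured clearance. The distortion would run in one direction, towards apparent loss of residual function on daily HD. Because samples under 80 ml are not sent for assay, analysis could not restore the missing clearances.

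**Working it through.** **Inputs.** Volume threshold: 80 ml (3.1.5). Minimum collection: 18 h (2.7, 3.1.5). Median session length: 3.50 h conventional, 2.36 h daily (Table 3). Sessions per week: 3 and 6.

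**Reproducing Table 3.** Average interval = 168 / sessions per week − session length:
- conventional: 168/3 − 3.50 = 52.5 h
- daily: 168/6 − 2.36 = 25.64 h

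Maximum interval:
- conventional: 72 − 3.50 = 68.5 h
- daily: 48 − 2.36 = 45.64 h

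All four figures agree with the table after rounding.

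**Midweek interval.** Section 3.1.5 prefers midweek collection, so this is the relevant gap:
- conventional: 48 − 3.50 = 44.5 h
- daily: 24 − 2.36 = 21.64 h

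**Implied cut-off.** Rate = 80 × 24 / collection hours, in mL/24 h.

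| Collection | Conventional | Daily | Ratio |
|---|---|---|---|
| 18 h in both arms | 106.7 | 106.7 | 1.0 |
| Full midweek gap (44.5 h; 21.64 h) | 43.1 | 88.7 | 2.06 |
| Full average gap (52.5 h; 25.6 h) | 36.6 | 75.0 | 2.05 |
| Full longest gap (68.5 h; 45.6 h) | 28.0 | 42.1 | 1.50 |

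With the 5th and 95th percentile weekly treatment times from Table 3 in place of the medians, the midweek ratio runs from 1.98 to 2.12.

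**One patient.** At 60 mL/24 h, a full midweek collection gives 60 × 44.5/24 = 111 ml on the conventional schedule (assayed) and 60 × 21.64/24 = 54 ml on the daily schedule (anuric, not assayed).

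**Against section 9.8.** 80 ml equals 100 mL/24 h only at 80/100 × 24 = 19.2 h. A sample can be anuric under 3.1.5 and exceed 100 mL/24 h only in collections of 18 to 19.2 h. At 18 h this means volumes above 75 ml (100 × 18/24) and below 80 ml. At 44.5 h, volumes from 80 ml to 185 ml (100 × 44.5/24) are not anuric under 3.1.5 but do not count as residual function under 9.8.

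**Eligibility.** 80 ml in 18 h is 80/(18 × 60) = 0.074 mL/min. Reaching the exclusion limit of 3 mL/min would need a urine-to-plasma urea ratio of about 3/0.074 = 40. At 44.5 h the ratio needed is about 100.

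**The case against.** The strongest reply is that the arm difference is conditional. Sections 2.7 and 3.1.5 ask for a timed collection of at least 18 hours within the interval, and only 6.2.3 describes collecting for the whole of it. If both arms collect for the same time, which 3.1.5 permits, the ratio is 1.0. This stands, and the twofold figure holds only for full-interval collection. It does not remove the problem, because nothing requires equal durations. A midweek daily collection can run only from 18 to about 21.6 h, while a conventional one can run from 18 to 44.5 h.

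A reader might infer that everyone between 37 and 75 mL/24 h is classified by arm. Those limits come from weekly average intervals. The preferred midweek gaps give 43 to 89 mL/24 h, and then only with full collection.

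A reader might also infer that 3.1.5 contradicts 9.8. The two cut-offs serve different uses: one labels anuria and triggers an assay, the other defines a baseline subgroup. Direct contradiction is confined to 18 to 19.2 h. The subgroup can be computed from volume and recorded time without an assay, and it is fixed while all patients are on three sessions a week.

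Finally, a reader might infer that the solute-clearance comparison under Objective 6 is materially biased. The protocol does not say that residual clearance enters that comparison, nor that an anuric patient's clearance is set to zero. As an illustration, assume a urine-to-plasma urea ratio of 5 to 10. Then 60 mL/24 h (0.042 mL/min) is a clearance of 0.2 to 0.4 mL/min, or roughly 0.06 to 0.12 weekly Kt/V units at V = 35 L (clearance × 10,080 min / 35,000 mL). Table 3 projects a separation in weekly stdKt/V of 3.82 − 2.46 = 1.36. The illustration is per affected patient, and the share of patients in the band is not given.

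**Conclusion.** The defect is real but minor. The anuria label and the decision to assay rest on a volume without a time base, and the protocol describes the collection period in two ways. With full midweek collection, as 6.2.3 implies, the cut-off at Months 4 and 12 is about 43 mL/24 h in the conventional arm and about 89 mL/24 h in the daily arm. In that band the rule can produce an apparent loss of residual renal function with daily HD. The documents do not show that it will, since this depends on how long patients actually collect.

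The consequence is limited to residual function in follow-up and its comparison between arms. At baseline the label varies with collection time but not with arm. Eligibility is practically unaffected, subgroup membership is not biased by arm, and residual function is neither a primary outcome nor listed among the secondary outcomes in Table 10.

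**What to change.** - In 3.1.5, classify anuria by a rate, volume × 24 / recorded collection hours, instead of a fixed 80 ml. Section 6.2.3 already has the collection time recorded.
- Reconcile 3.1.5 with 6.2.3 by setting one collection window for both arms that fits the daily midweek gap: at least 18 h and up to about 21 h. A 24 h target would not fit the 21.6 h gap.
- State the minimum volume for assay separately from the anuria label, so that samples now assayed are not lost. Using 100 mL/24 h as the assay rule would drop samples of 80 to 185 ml collected over 44.5 h. Keeping 80 ml as the assay minimum with shorter collections would also lose some: an output of 43.1 mL/24 h, now just assayed at 44.5 h, gives 43.1 × 18/24 = 32 ml at 18 h. The minimum should follow what the laboratory needs, which the protocol does not give.
- State how the rate in 3.1.5 relates to the 100 mL/24 h definition in 9.8. The choice of rate is the sponsor's.

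The cost is wording in two sections, one formula in the database, somewhat shorter collections in the conventional arm and a few more assays. No visit is added.

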## 3.1.6 Non-adherence and Deviations from the Protocol

If during follow-up subjects randomized to 6x/week therapy are unwilling or unable to continue to follow their 6x/week dialysis prescriptions stipulated by the protocol, efforts will be made to approximate the target 6x/week prescription as closely as possible with a revised prescription with either reduced total weekly treatment time or with a reduced frequency of dialysis sessions. The hierarchy of alternative options outlined in Table 7 below will be followed for patients unwilling or unable to adhere to the protocol 6x/week regimen.

In the event of a deviation from the 6x/week schedule specified by the protocol, the Clinical Center's personnel will consult with the study subject in an effort to adopt the highest option in the above table. If one of Options 1-4 is adopted, the Clinical Center's staff will periodically discuss the treatment options with the patient to determine if the patient is willing or able to return to a higher Option number, or ideally to return to the full 6x/week regimen specified by the protocol. Missed treatments will be monitored closely to ensure the safety of trial participants (Section 3.2).

# 3.2 Duration of Treatment and Follow-up

Each subject will be treated in his or her respective group for 12 months, or until death, a treatment stop-point is met, or loss to follow-up (see Section 7.3). The complete data collection procedures of the protocol will continue for the full 12 month follow-up period except for those subjects who die or are lost to follow-up. For subjects who relocate to a non-study dialysis unit, all attempts will be made to collect vital status, the primary and main secondary outcomes (see Section 5.1.2), and other centrally administered quality of life questionnaires at the 12-month assessment. When possible, the complete data collection procedures designated in the protocol will be maintained for subjects who switch to home HD. Those patients who are transplanted or switch to peritoneal dialysis will no longer be followed. Otherwise, no matter what happens to a patient, it is recommended that all attempts be made to encourage any subject who misses the two co-primary outcomes to provide these data for up to six months past his or her F12 window. Adverse events hospitalizations and serious adverse events should be recorded for an additional 30 days after the patients' F12 month ends. Starting with the first dialysis session held at least 30 days after the patients' F12 month ends, one week of data should be recorded from the dialysis unit's run sheets. This data will include start time, end time, and pre and post weight and blood pressure for each dialysis session held during the week.

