#### 7.3 Stop Points

It is recognized that certain situations may require premature discontinuation of the randomized therapy (stop-points). Provided the subject does not withdraw consent and is not lost to follow-up, data collection and follow-up will continue for all subjects meeting any of the following stop-points in order to perform the intent to treat analysis. Wherever possible and clinically appropriate, efforts should be made by the treating physician and principal investigator to get the patient back into their randomized group. All discontinuations of therapy will be reviewed by the Standards of Care/Clinical Management Committee, and all participants who permanently discontinue therapy will be interviewed regarding the reasons for discontinuation. Subjects may discontinue the randomized therapy for the following reasons:

- a) The treating physician determines that the subject requires more frequent or less frequent dialysis for reasons including, but not limited to, the following: uremic symptoms, uncontrolled hypertension, patient fatigue/burnout, etc.
- b) The subject changes from in-center hemodialysis to home hemodialysis. Where possible, recommendations will be made to continue the subject on their assigned

treatment frequency (i.e., in-center daily will change to home daily HD; in-center conventional will change to home conventional HD).

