#### 7.4 Losses to Follow-up

Efforts will be made to follow all randomized subjects for 12 months, irrespective of their adherence to the randomized therapy. However, certain situations may preclude complete data collection for the full 12 months (losses to follow-up).

The randomized therapy and routine data collection will be discontinued in the following situations:

- a. Subject withdraws consent for data collection
- b. Subject changes to peritoneal dialysis
- c. Subject receives renal transplant
- d. Subject relocates to a non-study center.
- e. Subject changes to home HD.

For patients who are lost to routine data collection for reasons b - e above, all attempts will be made to collect vital status. For patients who are lost to routine data collection for reasons d and e above, all attempts will be made to collect vital status, the primary and main secondary outcomes, and other centrally administered quality of life questionnaires at the 12-month visit.

All losses to follow-up with reason will be reported to the DCC (discontinuation of therapy form). The Adherence Committee will review all losses to follow-up on a monthly basis.

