#### 9.4 Main Secondary Outcomes

As described in Section 9.3, the PHC/Mortality and LV mass/Mortality composites are the coprimary endpoints for evaluation of patient benefit in the trial. In addition, as described in Section 5.1.2, main secondary outcomes have also been designated for each of seven specific and conceptually distinct physiological or quality of life-related outcome domains. These include: i) change over 12 months in the PHC; and, ii) change over 12 months in LV mass (without the mortality components), which represent the main secondary outcomes for evaluation of the physical function and cardiac structure and function domains, respectively. The remaining outcome domains and associated main secondary outcomes are iii) depression/disease burden (change over 12 months in Beck Depression Inventory), iv) nutrition (change over 12 months in serum albumin), v) cognitive function (change over 12 months in the Trail Making Test B), vi) mineral metabolism (change over 12 months in average pre-dialysis phosphorus), and vii) clinical events (rate of nonaccess hospitalizations or death). The primary evaluation of the effects of the treatment interventions on each of these seven outcome domains will be based on the designated main secondary endpoints. Analyses of other outcomes within each domain will be regarded as exploratory. Hypertension and anemia are also stipulated as main outcome domains, but are not conducive to the designation of a single main endpoint.

Two-sided tests will be used when testing the effects of the interventions on both the primary and secondary endpoints. The primary and main secondary analyses will be conducted by intention-to-treat in the sense that all patients analyzed according to their randomized assignment, irrespective of whether they adhered to the interventions. As noted above, however, follow-up will be censored at the time of renal transplantation. The analyses of the main secondary endpoints will be tested at the 0.05 level, without formal adjustment for multiple comparisons. However, nominally significant

effects on individual secondary outcomes will be interpreted as consistent with Type I errors unless accompanied by significant effects of the interventions on the primary outcomes and a consistent pattern of treatment effects across multiple secondary outcomes.

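### Protocol Sections 3.2 and 7.4 conflict on follow-up after a switch to peritoneal dialysis, so a later death may be censored or counted in both co-primary composites

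*Protocol*

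**What the plan says.** **PD.** Section 3.2 ends follow-up: "Those patients who are transplanted or switch to peritoneal dialysis will no longer be followed". Section 7.4 lists change to PD as reason b under this lead-in: "The randomized therapy and routine data collection will be discontinued in the following situations". It then adds: "For patients who are lost to routine data collection for reasons b - e above, all attempts will be made to collect vital status". Its further promise, to seek the primary and main secondary outcomes at month 12, covers only reasons d (relocation) and e (home HD). Section 7.3 does not mention PD.

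**Home HD.** Section 3.2 says: "When possible, the complete data collection procedures designated in the protocol will be maintained for subjects who switch to home HD". Section 7.3(b) makes it a stop-point ("The subject changes from in-center hemodialysis to home hemodialysis"), and for stop-points "data collection and follow-up will continue for all subjects meeting any of the following stop-points in order to perform the intent to treat analysis". Section 7.4 lists the same event as a loss: "e. Subject changes to home HD".

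**Analysis.** Section 9.3 censors a patient before month 12 for transplant or for loss to follow-up for mortality. It censors at month 12 a survivor who has no month-12 measurement. Section 9.4 analyses patients by randomized assignment, "irrespective of whether they adhered to the interventions", and repeats that follow-up is censored at transplant. Section 9.6 censors the non-access hospitalization or death outcome at transplant, at transfer to a nonparticipating facility, or at 12 months. Neither PD nor home HD is named in 9.3 or 9.6.

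**The concern.** In the co-primary composites a death takes one of the lowest ranks, while a censored patient only leaves the risk set. Whether a PD switcher's death is known depends on which section a site follows. An analysis plan can fix the coding, but it cannot recover vital status that sites were told not to collect.

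The loss may also be related to treatment. Section 5.2.4 counts a change to PD as a measure of patient burn-out, which it treats as a potential risk of daily HD. Section 2.5.2 excludes patients already scheduled for PD, so a switch during the trial is largely an unplanned event after randomization. Sections 2.8 and 7.1 promise evaluation of every randomized patient regardless of adherence or time on the regimen. Stopping at PD sits badly with that promise.

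**Working it through.** **1. The rules side by side, for the co-primary composites**

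| Patient | Section 3.2 | Section 7.4 | Status under 9.3 |
|---|---|---|---|
| PD, dies before month 12 | Not followed | Vital status sought | Censored at the switch (3.2) or death ranked by survival time (7.4) |
| PD, alive at month 12 | Not followed | Vital status sought, PHC and LV mass not sought | Censored at the switch (3.2) or at 12 months, above all deaths (7.4) |
| Home HD, dies | Full collection when possible | Vital status sought | Death under both, and under 7.3 |
| Home HD, alive | Full collection when possible | Month-12 primary outcomes sought | Measured change, if obtained, under both and under 7.3 |
| Transplant | Not followed | Vital status sought | Censored at transplant by 9.3 and 9.4 either way |

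Only the PD rows give two answers.

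**2. The plan's own power figures**

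Inputs from Section 9.11: 250 patients, 125 per arm; control mortality 12%/yr; a 20% reduction, so 0.12 × 0.8 = 0.096/yr in the daily arm; transplant 4%/yr; 80% measured at month 12; LV mass SD 24 g; Hochberg procedure. The PHC SD follows from the Table 15a footnote: 2.28 / 0.25 = 9.12. The log-rank composite was simulated with 3,000 replicates and no effect on the other outcome.

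| Composite | Effect | Stated power | Simulated power |
|---|---|---|---|
| PHC | 4.28 units | 0.80 | 0.791 |
| PHC | 4.96 units | 0.90 | 0.907 |
| LV mass | 11.3 g | 0.80 | 0.776 |
| LV mass | 13.0 g | 0.90 | 0.882 |

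The Monte Carlo standard error is about 0.008. The PHC figures reproduce. LV mass runs about 2 points low, which is close enough to use the model for comparing the two rules.

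**3. How many deaths change status**

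The protocol gives no PD-switch rate, so λ = 1%, 2%, 5% and 10% per year are assumptions. The competing hazard is 0.12 + 0.04 = 0.16, and the share of it due to death is 0.12 / 0.16 = 0.75.

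- Switchers = 250 × λ/(λ + 0.16) × (1 − e^−(λ+0.16))
- Deaths after a switch and before month 12 = 250 × 0.75 × [λ/(λ + 0.16) × (1 − e^−(λ+0.16)) − e^−0.16 × (1 − e^−λ)]

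At λ = 0.10, switchers are 250 × 0.3846 × 0.2289 = 22.0. Deaths after a switch are 187.5 × (0.08806 − 0.85214 × 0.09516) = 187.5 × 0.00697 = 1.31.

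| λ per year | Switchers of 250 | Deaths after switch |
|---|---|---|
| 1% | 2.3 | 0.13 |
| 2% | 4.6 | 0.27 |
| 5% | 11.3 | 0.66 |
| 10% | 22.0 | 1.31 |

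Expected deaths in all are 125 × [0.75 × (1 − e^−0.16) + (0.096/0.136) × (1 − e^−0.136)] = 25.1. At most about 1.31 / 25.1 = 5% of deaths change status over this range.

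**4. Power under each rule**

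For the LV mass composite at 11.3 g, power under 3.2 and 7.4 is 0.785 and 0.784 (λ = 1%), 0.782 and 0.782 (2%), and 0.785 and 0.785 (5%); 10% was not simulated. These runs use the same switch rate in both arms, unrelated to prognosis, and hold the measured share at 80%. They isolate the death coding. They do not measure bias from switching that differs by arm, or from the missing month-12 values.

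**5. Hospitalization outcome**

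Section 9.6 justifies censoring at transplant and transfer by the fact that hospitalizations are not recorded afterwards. Section 7.4 also stops routine collection at PD and home HD, yet 9.6 does not censor there. Time at risk may then accrue without recorded hospitalizations, which would lower the apparent rate in the arm with more switching.

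**The case against.** The strongest reply is that little hangs on this. Few patients should switch to PD, since planned changes are excluded at entry. Patients who cannot sustain six sessions have the stepped options of Section 3.1.6, or stop-points with continued follow-up, so most treatment failures stay observed. Section 9.9 admits that losses will occur and plans pattern-mixture sensitivity analyses. All of this stands, and it is why the effect is rated small. It does not tell a site whether to ascertain a PD switcher's death.

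Section 3.2 also recommends pursuing missed co-primary outcomes for up to six months past the month-12 window. That recommendation is worded as applying to patients other than those transplanted or switched to PD, so it does not fill the gap. Section 9.6's transfer rule may catch a switcher who also changes facility, but not one who stays.

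A reader might infer more than the text supports:

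- **That the death-or-censored ambiguity extends to home HD.** It does not: 3.2, 7.3 and 7.4 all keep or seek vital status and the primary outcomes there.
- **That 9.4 makes transplant the only exception to intention-to-treat, so losing PD switchers breaks it.** Section 9.3 also censors patients lost to follow-up for mortality and survivors without a measurement, and 9.4 refers back to it.
- **That a bias in PHC points can be quoted.** The protocol gives no switch rate by arm and no outcome deficit among switchers, and a difference in means is not the log-rank test. On the missing PHC itself, 3.2 and 7.4 do not conflict: neither collects it.
- **That the discontinuation figures in 5.2.4 (median 41%) are a PD rate.** They cover discontinuation of daily HD for any reason.

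**Conclusion.** The PD contradiction between 3.2 and 7.4 is real and reaches both co-primary composites: a death is censored or counted, and a survivor is censored at the switch or at month 12. Both sections also leave the month-12 PHC and LV mass of PD switchers uncollected, against the follow-up promised in 2.8 and 7.1. The home HD conflict (7.3(b) and 3.2 against 7.4(e)) is real too, but touches routine interim data and possibly hospitalizations, not co-primary deaths. Section 9.6 is out of step with 7.4 for both modality changes.

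The likely effect on the primary result is small: about 0.1 to 1.3 deaths of some 25, with LV mass composite power unchanged to 0.1 point at 1% to 5% per year. This rests on assumed switch rates, on 12%/yr mortality applied to all 250 patients, and on mortality that does not change with the switch. It would be larger if switchers were sicker or if switching differed by arm. Severity is moderate: an undetermined event rule and avoidable missing data, not lost power.

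**What to change.** - **Section 3.2:** delete the PD clause. The same edit can settle vital status after transplant, where 3.2 and 7.4 also differ without affecting the co-primary composites.
- **Section 7.4:** for PD switchers, seek vital status, the telephone SF-36 and the month-12 MRI, as it already does for the primary outcomes after relocation and home HD.
- **Home HD:** state the data collection rule once, in either 7.3 or 7.4. The two sections also disagree on whether randomized therapy continues after this change. The sponsor must reconcile them; this review does not choose the rule.
- **Sections 9.3 and 9.6:** name PD and home HD and align censoring with what is collected. For 9.6, either record hospitalizations after these changes or end hospitalization time at risk when recording ends. Continued recording is preferable, because censoring at a change of modality may be informative.

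The cost is protocol wording plus a few month-12 assessments that are already on the schedule for every randomized patient: for about 2 to 22 PD switchers at most, at the assumed rates.
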